3 INVESTIGATIONAL PLAN

3.1 Overall Study Design and Plan

ABX464-401 is a phase 2/3 study evaluating the efficacy and safety of ABX464 50mg once daily (QD) (oral capsule), on treating inflammation and preventing acute respiratory failure in patients infected with SARS-CoV-2.

Eligible patients will be randomized according to a 2:1 ratio into 2 treatment cohorts as follows:

[figure not shown]
- Standard of Care (SoC) + ABX464 50mg QD cohort: 533 patients
- Standard of Care + Placebo QD cohort: 267 patients

Upon randomization, patients will be stratified according to:

- Age ≥ 65 years or < 65 years (with at least one risk factor)
- Inpatient or outpatient, at the time of enrolment

The study will consist of 3 periods:

- Treatment phase: randomized patients will be treated for 28 days
- Safety follow-up phase of 21 days
- Exploratory follow-up of the pulmonary function 3 months after the last study drug intake.

* Considering sites potential organization and the quarantine requirements in participating countries, randomization visit can be splitted into 2 separated visits. However, the interval between these 2 visits cannot exceed 48 hours to ensure patients start the study treatment at an early stage of the disease.

From Day 0 onwards, randomized patients will be followed by the investigational site at 7 days (D7 +/- 2 days), 14 days (D14 +/- 2 days), 21 days (D21 +/- 2 days), 28 days (D28 +/- 2 days) and finally at 48 days (D48 +/- 2 days), after randomization.

A long-term follow-up is scheduled as an onsite visit for patients having been hospitalized during the course of the study. This follow-up will be performed 3 months after the last study drug intake and will consist of a respiratory function exploration. In addition, investigators will report the disease severity rating using a 7-point ordinal scale.

An independent DSMB, with expertise and experience in virology and immunology, and without direct involvement in the conduct of the trial, will be set up specifically to guarantee effective protection of patients, ensure the ethical conduct of the trial, benefit/risk ratio of the trial, and to ensure the independent review of the scientific results during the trial and at the end of the trial. The DSMB will meet first after the 20 first patients are enrolled and treated for at least 4 weeks (D28) and then every month after this first meeting.

A study steering committee will oversight the practical aspects of the study especially with regards to the evolving nature of the COVID-19 infection. The Steering Committee will work in conjunction with the DSMB. The Steering Committee will be able to terminate the trial if the medical relevance of the MiR-Age is substantially modified during its execution. ABIVAX and principal investigator will agree, in writing prior to the start of the study, to the charter of the Steering Committee.

One interim analysis is planned after approximately 300 of randomized patients' complete day 28 assessment or long term follow up period. Interim analysis will be performed without unblinding the sponsor as part of DSMB activities. The purposes for the interim analysis are to:

- assess the safety of the study treatment,
- potentially stop the study early due to efficacy/futility, or
- adjust the sample size.

3.2 Endpoints

3.2.1 Primary Efficacy Endpoint

Not applicable(refer to Section 4.13).

3.2.2 Secondary Efficacy Endpoints

Not applicable(refer to Section [4.13](#)).

3.2.3 Safety Endpoints

- Physical examinations
- Vital signs (supine blood pressure [BP] and pulse, oral body temperature, SpO2)
- 12-lead electrocardiograms (ECG): Investigator interpretation
- Clinical laboratory tests (hematology and chemistry)
- Adverse event (AE) assessments
- Concomitant medication assessments

3.2.4 Exploratory Endpoints

Not applicable(refer to Section [4.13](#)).

4 STATISTICAL METHODS

4.1 Data Quality Assurance

All tables, figures and data listings to be included in the report will be independently checked for consistency, integrity and in accordance with standard Parexel procedures.

4.2 General Presentation Considerations

The overall outline of the scheduled assessment and other study procedures can be found in [Table 3 Schedule of Assessments](#). In the following, the data handling conventions should be interpreted within the framework of the Schedule of Assessment.

4.2.1 Study Days

The date of Visit 1 is defined as Day 1. All other study days will be labeled relative to Day 1.

For observation/event dates on or after Day 1, study day for an observation/event date is derived as:

- Observation/event date – Visit 1 date + 1 day, which could be Day 1, Day 2, Day 3, etc.

For observation/event dates prior to Day 1, study day for an event date is derived as:

- Observation/event date – First infusion date, which could be Day -1, Day -2, etc., referring to 1 day, 2 days, etc., prior to Day 1, respectively.

Subsequently, Day 0 is not defined.

4.2.2 Definition of Baseline and Post-baseline Assessments

Baseline (derived) is defined as the last available assessment (scheduled or unscheduled) on Day 1. Assessments performed after Day 1 are considered post-baseline assessments.

Change from Baseline is derived where both baseline and post-baseline values are available:

- Change from Baseline = post-baseline value – Baseline value

End of Treatment (EoT) assessment is defined as the last available assessment (scheduled or unscheduled) assigned to treatment period.

End of Study (EoS) assessment is defined as the last available assessment (scheduled or unscheduled).

4.2.3 Analysis Periods, Visit Windows and Naming

Analysis periods will be derived for the statistical analyses based on the assigned analysis visits. Timing of analysis periods with start and end visits are tabulated in [Table 1](#).

Table 1 Analysis Periods

Analysis Period	Start	End
Treatment Period	Visit 1 (Day 1)	Visit 5
Safety Follow-up Period	Visit 5 + 1 day	Visit 6
Long-term FUP	Visit 6 + 1 day	Visit 7
Overall Study Period	Visit 1 (Day 1)	Visit 7

As patients will not necessarily have their examinations at the exact scheduled visit time, it could be misleading if all data with the same nominal visit number are lumped together for a by-visit analysis. Thus, all post-baseline data (including both scheduled and unscheduled visits) will be “realigned” in the statistical analysis according to the appropriate window schema and according to the following general conventions.

The reference start day of the first visit window in the Treatment Period is Day 1. The start day of all other visit windows up to Visit 5 (Day 28) is the midpoint between the scheduled visit day for the previous visit ($Visit_{(i)}$) and the subsequent visit ($Visit_{(i+1)}$) plus 1 day: $(Visit_{(i)} + Visit_{(i+1)})/2 + 1$.

The end day of a visit window in the Treatment Period is the day prior to the start day of the next visit window with the exception of the last visit window, where the end day of the visit window will be the day of the EoT visit.

Safety Follow-up Period: Visit 6 (EoS) and Visit 7 (Long term FUP) assessments will be realigned utilizing the same general conventions but with the reference start day of the safety follow-up period derived relative to the last available assessment (scheduled or unscheduled) assigned to Treatment Period + 1 day (see [Table 2](#)).

Width of a realigned visit window will depend on the schedule of assessments for the respective type of assessment. That is, $Visit_{(i)}$ and $Visit_{(i+1)}$ day above refer to the visits as scheduled for the respective assessment and unless otherwise specified will be realigned per [Table 2](#) (General realignment of visits).

Multiple assessments within visit windows

For visit windows multiple records may exist in one particular visit window for a particular assessment (i.e. laboratory assessments). The assessment closest to the actual target visit day is chosen as the analyzable record for both continuous variables and categorical variables. If two assessments have the same distance, then the earlier one by relative study day will be chosen as the analyzable record.

Early discontinuation visit remapping

Patients who prematurely discontinue from the study for any reason, will be scheduled for a Safety follow-up visit approximately 21 days following their last study drug intake, at which time all of the assessments listed for that visit will be performed. This visit will be assigned to Visit 6 (EoS).

Table 2 Visit Windows

Study Period	Visit Name	Target Visit Day	Start Day of Visit Window	End Day of Visit Window
Treatment	Visit 1	Day 1	1	1

Study Period	Visit Name	Target Visit Day	Start Day of Visit Window	End Day of Visit Window
	Baseline	Defined as the last available assessment (scheduled or unscheduled) on Day 1		
	Visit 2	Day 7	2	10
	Visit 3	Day 14	11	18
	Visit 4	Day 21	19	25
	Visit 5 (EoT)	Day 28	26	Date of study drug return.
	End of Treatment	End of Treatment is defined as the last available assessment (scheduled or unscheduled) assigned to Treatment Period.		
Safety Follow-up	Visit 6	Day 48	Date of study drug return + 1 day	Target visit day + 30 days
	Visit 7 (Long-term FUP)	Date of study drug return + 90 day	Target visit day - 10 days	Target visit day + 30 days
	End of Study	End of Study is defined as the last available assessment (scheduled or unscheduled) assigned to the Overall Study Period.		

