7. STUDY COMPLETION

7.1. Patient Completion

Treatment with ABX464/Placebo shall continue until D28, except if a patient fulfils a premature discontinuation criterion (defined below).

Patients should be instructed to take their last study drug dose until the day before D28 visit. Should a patient start to take the treatment at D1, s/he will be instructed to take the last dose on D28.

After D28, patients will come back 21 days after the last study drug intake to perform an onsite safety follow-up visit at D48.

Following this visit, long-term follow-up for respiratory function exploration will be performed on-site for patients having been hospitalized during the study. This follow-up will take place 3 months after the last study drug intake.

For outpatients, a remote telephone follow-up will be performed 3 months after the last study drug intake.

Then, patients will exit the study and will be treated/follow-up according to the site standard of care.

Given the fact that the pulmonary function follow-up is exploratory and depends on the patient status during the study, a patient status is COMPLETE when the treatment period of 28 days is fulfilled, and the safety follow-up of 21 days is performed.

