7.2. Patient Premature trial discontinuation

A patient can be withdrawn at any time from the study. Premature trial discontinuation could occur for the following reasons:

- Investigator's decision.
- An Adverse Event or an intercurrent condition that preclude continuation of treatment. Specifically, an elevation $\geq 3.0 \times$ ULN in liver transaminases (AST/SGOT and/or ALT/SGPT) or Alkaline phosphatase or in total bilirubin compared to baseline requires close observation with repeating liver enzymes and serum bilirubin tests every 2 days. Discontinuation of the study treatment should occur if:
 - ALT or AST $> 8 \times$ ULN
 - ALT or AST $> 3 \times$ ULN and total bilirubin $> 2 \times$ ULN or INR > 1.5
 - ALT or AST $> 3 \times$ ULN with appearance of fatigue, nausea, vomiting, right upper quadrant pain or tenderness, fever, rash, and/or eosinophilia ($> 5\%$).
 - Alkaline Phosphatase $\geq 2.0 \times$ ULN
- Serious adverse event with suspected causal relationship to the IMP
- Any relevant toxicity or negative change in the risk/benefit assessment leading to an unacceptable risk for the patient (i.e. occurrence of adverse events which character, severity or frequency is new in comparison to the existing risk profile), or any data deriving from other clinical trials or toxicological studies which negatively influence the risk/benefit assessment.
- Major protocol violation.
- Withdrawal of consent.
- Administrative reasons from Sponsor.

A patient who prematurely exits the study will not be replaced.

All patients, regardless of the completion or premature discontinuation, should come back for an on-site safety follow-up visit 21 days after the last study drug intake, and all examinations must be performed according to the study flow-chart.

The same long-term follow-up will be performed as described in section 7.1 providing the reason for premature discontinuation is not "withdrawal of consent".

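### SAP Table 2 uses the bottle-return date as the boundary between end of treatment and safety follow-up, and this fails when the bottle comes back very late, early or never

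*SAP*

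**What the plan says.** SAP section 4.2.3 describes the same boundary in several ways.

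- Table 2 starts Visit 5 (EoT) on Day 26 and ends it on "Date of study drug return". Visit 6 starts on "Date of study drug return + 1 day" and ends at "Target visit day + 30 days", which for the Day 48 target is Day 78. The Visit 7 target is "Date of study drug return + 90 day", with a window from 10 days before to 30 days after.
- The text makes an exception for the last treatment window, "where the end day of the visit window will be the day of the EoT visit". It starts the follow-up period the day after the last assessment assigned to treatment.
- Table 1 starts safety follow-up the day after Visit 5.

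The protocol uses a different anchor for follow-up. Under section 7.2 all patients, including those who stop early, "should come back for an on-site safety follow-up visit 21 days after the last study drug intake". On the long-term visit, section 7.1 says: "This follow-up will take place 3 months after the last study drug intake".

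The protocol expects the bottle back at the end-of-treatment visit (sections 5.2.5 and 6.4), and the flow chart schedules accountability only at D28. The SAP also has a remapping paragraph that assigns the safety visit of patients who leave the study early to Visit 6.

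**The concern.** Bottle return is a logistics date. It marks the end of treatment only if the patient brings the bottle to the right visit. Table 2 nevertheless makes it decide which assessments count as treatment and which as follow-up.

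SAP version 5.0 is a safety-only plan. Its laboratory, vital-sign and ECG tables are all by visit (sections 4.11.3 and 4.11.4), so the windows decide which values appear under Visits 5 and 6. Section 4.2.2 defines End of Treatment as the last assessment assigned to the treatment period, so a period that closes late can take in an off-drug value. Two programmers following different sentences of section 4.2.3 could also produce different tables.

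**Working it through.** **Inputs.** SAP section 4.2.1 makes Visit 1 Day 1 with no Day 0, so protocol D28 is SAP Day 29 and D48 is SAP Day 49. A completer's last dose is the day before the D28 visit (protocol 7.1), which is SAP Day 28. The Visit 7 tolerance is ±7 days (protocol 5.2.7). Three months is taken as 91 days, which is an assumption. R is the SAP day of bottle return.

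**Reproducing Table 2.** The midpoint rule gives a Visit 5 start of (21 + 28)/2 + 1 = 25.5, which rounds up to the tabulated Day 26. The other tabulated start days do not follow one rounding rule (the formula gives 5, 11.5 and 18.5; the table has 2, 11 and 19), but this does not affect the present point.

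**Windows as functions of R.** Visits 2, 3 and 4 are fixed at Days 2–10, 11–18 and 19–25. The others are:

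- Visit 5 = [26, R]
- Visit 6 = [R + 1, 48 + 30] = [R + 1, 78]
- Visit 7 = [R + 90 − 10, R + 90 + 30] = [R + 80, R + 120]

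| R | Visit 5 | Visit 6 | Visit 7 | Result |
|---|---|---|---|---|
| 15 | empty | 16–78 | 95–135 | Visit 6 overlaps Visits 3 and 4 |
| 29 | 26–29 | 30–78 | 109–149 | as intended |
| 35 | 26–35 | 36–78 | 115–155 | Visit 5 and 6 records unchanged |
| 49 | 26–49 | 50–78 | 129–169 | safety visit lies in Visit 5 |
| never | no end | no start | no target | undefined |

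**Case 1, return at or after the safety visit.** With R = 49 the safety visit on Day 49 is 49 − 28 = 21 days after the last dose. It falls in the treatment period and becomes the End of Treatment record. Visit 6 (Days 50–78) contains no scheduled visit.

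**Case 2, early return.** Visit 5 is empty when R ≤ 25. Visit 6 overlaps at least one of Visits 2–4 when R + 1 ≤ 25, that is R ≤ 24. With R = 15, a visit on Day 22 fits both Visit 4 and Visit 6, and an attended D28 visit (Day 29) fits only Visit 6. The closest-to-target rule chooses among records within one window. It does not choose between windows.

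**Case 3, no return.** Visit 5 end, Visit 6 start and the Visit 7 target all need R. SAP section 4.9 gives exposure a fallback to date of death. Table 2 has no fallback.

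**Visit 6/7 gap.** For R = 29, Days 79–108 (30 days) belong to no window. The D48 visit with its ±2 days falls on Days 47–51 and an on-time Visit 7 on 28 + 91 ± 7 = Days 112–126, so no scheduled visit lies in the gap.

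**Visit 7.** For R = 49 the window opens on Day 129, after the whole on-time range of Days 112–126.

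**The case against.** The strongest reply is that by design bottle return and the EoT visit are the same event, so Table 2 and the text normally give the same date. That stands: for on-schedule return (about Days 27–31) there is no overlap, no empty window and no misfiled visit.

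A reader might infer more than the documents support:

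- *That every off-schedule return misfiles data.* It does not. A return on Day 35 leaves the Day 49 visit in Visit 6 and the Visit 5 record unchanged.
- *That early leavers' safety visits are filed as end of treatment when the bottle comes back at that visit.* The remapping paragraph sends them to Visit 6, and section 4.2.3 lets a specific rule override Table 2. That paragraph covers patients who discontinue the study. It does not cover completers, or patients who stop drug but keep attending.
- *That a late return replaces the Visit 5 value.* An attended D28 visit is closer to Day 28 and remains the Visit 5 record.
- *That safety conclusions in general are at risk.* Adverse event tables split at Day 28 and do not use these windows.
- *That the gap or Visit 7 loses important data.* No scheduled visit lies in the gap. The only laboratory item at Visit 7 is haemoglobin, tied to the optional diffusing-capacity test, and the other Visit 7 analyses were removed (section 4.13).
- *That the arms are affected differently.* Nothing in the documents shows this.

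Sections 4.11.3 and 4.11.4 also name no separate End of Treatment table. That record is defined, but it is not shown to reach a planned output. The missing Visit 6 value in Case 1 does reach planned tables.

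**Conclusion.** The point holds as a specification defect of limited reach. Section 4.2.3 gives conflicting boundaries, and Table 2, followed as written, misfiles scheduled assessments or leaves them ambiguous or without a window in three situations: a completer's return at or after the safety visit, return on or before Day 25, and no return.

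The effect is limited to descriptive by-visit laboratory, vital-sign and ECG summaries and to the End of Treatment record. How many patients fall into the three cases is not stated, so no numerical size can be given. Case 2 matters mainly for patients who hand the bottle back early and still attend later scheduled visits. The Visit 7 dates rest on the 91-day assumption.

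**What to change.** In SAP section 4.2.3:

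- Replace the drug-return date in Table 2 with the day of the EoT visit, which is the text's own rule, or with the last-dose date if there was no EoT visit. Open Visit 6 the next day and align Table 1 and the text.
- State that the safety visit about 21 days after last intake always goes to Visit 6, including for patients who stop drug early.
- State that Visits 2–4 keep their fixed windows ahead of Visit 6.
- Anchor the Visit 7 target to last study drug intake.
- Express every target and window on the SAP Day 1 scale (D28 becomes Day 29, D48 becomes Day 49).

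For a completer who returns the bottle on Day 49, this gives Visit 5 = Days 26–29 and Visit 6 from Day 30, so the safety visit falls in Visit 6. Visit 7 has target 28 + 90 = Day 118 and window Days 108–148, which contains the on-time range of Days 112–126. A Visit 6/7 gap remains but contains no scheduled visit.

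Extending the midpoint rule to Visit 5 is less suitable. Visit 6 would start at (28 + 48)/2 + 1 = Day 39, so Visit 5 would run to Day 38 and admit values up to 10 days after a Day 28 last dose. A midpoint between Visits 6 and 7 also does not suit vital signs and ECG, which have no Visit 7.

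The cost is SAP wording and one derivation change. SAP sections 4.5.1 and 4.8 already rely on treatment duration and a treatment completion or withdrawal date, so an anchor appears to be available. Because section 4.9 derives exposure from the return date, a few last-dose dates may have to be estimated.

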4.2.4 Analysis Conventions

Continuous data will be summarized in terms of the mean, standard deviation (SD), median, minimum, maximum and number of observations, unless otherwise stated. The minimum and maximum will be reported to the same number of decimal places as the raw data recorded in the database. The mean and median will be reported to one more decimal place than the raw data recorded in the database. The SD will be reported to two more decimal places than the raw data recorded in

the database. In general, the maximum number of decimal places reported shall be four for any summary statistic.

Categorical data will be summarized in terms of the number of patients providing data at the relevant time point (n), frequency counts and percentages. Any planned collapsing of categories will be detailed in the SAP text and the data displays.

Percentages will be presented to one decimal place. Percentages will not be presented for zero counts. Percentages will be calculated using n as the denominator. If sample sizes are small, the data displays will show the percentages, but any textual report will describe frequencies only.

Changes from baseline in categorical data will be summarized using shift tables where appropriate.

4.3 Handling of Dropouts or Missing Data

4.3.1 Imputation of Missing and Incomplete Dates/Times

Every effort will be made to collect complete dates for all study assessments. The following date imputation rules will be applied for missing or partial dates:

- If month and year available, set start date to latest of (1st of the month, first dose date), if end date is complete and imputed start date > end date, set imputed start date to end date – 1
- If year available: Set start date to latest of (January 1st, first dose date), if end date is complete and imputed start date > end date, set imputed start date to end date – 1
- If start date is completely missing, set to first dose date, if end date is complete and imputed start date > end date, set imputed start date to end date – 1.

Completely missing time information will be imputed as 00:00. Partially missing time information with missing hour (xx:mm) or minute (hh:mm) part will be imputed as 00:mm or hh:00, respectively. Missing part will be shown as NK in the listings (where NK = Not Known).

If time is not collected and date of assessment is the same as the first dose date, then assessment will be assumed to be collected prior to treatment unless schedule of assessments and protocol indicate planned collection is always after dosing.

Any AEs with incomplete start and end dates/times will be treated as follows:

Adverse events with unknown start and/or end times (but where the date is known) will be imputed with a time of 00:00 h for the tabulations but will be shown as NK: NK in the listings (where NK = Not Known).

Adverse events with completely unknown start dates will be considered as treatment-emergent for the tabulations and will be shown as NK in the listings. Partially complete AE dates will not be imputed in the listings and the available day, month and year components will be used to determine if an adverse event is treatment-emergent taking the first dosing date and end of study date as references.

Imputing partial AE and prior/concomitant medication start dates:

- a) If the year is unknown, the date will not be imputed and will be assigned a missing value.
- b) If the month is unknown, then:
 1. If the year matches the first dose date, then impute to the month and day of the first dose date.
 2. Otherwise, assign 'January'.
- c) If the day is unknown, then:
 1. If the month and year match the first dose date, then impute to the day of the first dose date.
 2. Otherwise, assign '01'.

Imputing partial AE and prior/concomitant medication stop dates:

- a) If the year is unknown, the date will not be imputed and will be assigned a missing value.
- b) If the month is unknown, then assign 'December'.
- c) If the day is unknown, then impute to the last day of the month.

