8. ADVERSE EVENTS (AE) AND SERIOUS ADVERSE EVENTS (SAE)

The investigator is responsible for the detection and documentation of events meeting the criteria and definition of an AE or SAE. During the study, in case of a safety evaluation, the investigator or site staff will be responsible for reporting AEs and SAEs, as detailed in this section of the protocol.

All adverse events (Serious and non-serious) will be collected from the time of signing of ICF and until D48 visit.

Any disease progression will be both reported in the eCRF as an adverse event and documented in the efficacy section.

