4.11.1 Adverse Events

Adverse events (AEs) will be coded using the Medical Dictionary for Regulatory Activities (MedDRA) Version 23.0 and the Common Terminology Criteria for Adverse Events (CTCAE) Version 5.0.

An AE is any untoward medical occurrence in a study patient administered an IMP which does not necessarily have a causal relationship with this treatment. An AE can therefore be any unfavorable and unintended sign (including a clinically significant abnormal laboratory finding), symptom, or

disease temporally associated with the use of an IMP, whether or not considered related to the IMP. Adverse events may include the onset of new illness and the exacerbation of pre-existing conditions.

Other untoward events occurring in the framework of a clinical study will be recorded as AEs, e.g. those occurring during treatment-free periods (including post-treatment Follow-up period), in association with study-related procedures and assessments.

Concomitant illnesses, which existed before entry into the clinical study, will not be considered AEs unless they worsen during the treatment period. Pre-existing conditions will be recorded as part of the patient's medical history.

A treatment-emergent adverse event (TEAE) is defined as an AE that begins or that worsens in severity after at least one dose of the study drug has been administered.

Adverse event leading to study discontinuation is defined as an AE ongoing on the date of study discontinuation. Ongoing is defined as an AE started on or before and ended on or after the date of study discontinuation.

Summaries with number and percentage of patients reporting at least one adverse event and the total number of events will be reported by group and overall. Adverse event summaries will be provided separately for adverse events which occur or worsen from first dosing to Day 28 and adverse events which occur or worsen after Day 28.

- An overview on the number and percentage of patients with:
 - Any AE
 - Any AE of Grade 3 or higher
 - Any TEAE
 - Any TEAE of Grade 3 or higher
 - Any serious AE (SAE)
 - Any serious adverse drug reaction (SARs)
 - Any suspected unexpected serious adverse reaction (SUSARs)
 - Any treatment-emergent SAE
 - AE leading to death
 - TEAE leading to death
 - TEAE leading to treatment withdrawal
 - Any AE leading to study discontinuation

- TEAE leading to study discontinuation

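### Setting unknown AE start times to 00:00 can class untimed first-dose-day events as pre-dose and drop them from the TEAE tables, depending on a comparison the SAP never states

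*SAP*

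**What the plan says.** SAP 4.3.1 has several rules that bear on AE timing:

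- **Date known, time unknown:** the AE "will be imputed with a time of 00:00 h for the tabulations". Listings show the time as not known.
- **General rule for times:** "Completely missing time information will be imputed as 00:00".
- **No start date:** "Adverse events with completely unknown start dates will be considered as treatment-emergent for the tabulations".
- **Partial date:** the available date components decide "if an adverse event is treatment-emergent taking the first dosing date and end of study date as references". For an unknown day, the imputation rule is: "If the month and year match the first dose date, then impute to the day of the first dose date".
- **Untimed assessments on the dosing day:** a separate rule opens "If time is not collected and date of assessment is the same as the first dose date" and defaults to pre-treatment. It is worded for assessments, not AEs.

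SAP 4.11.1 defines a TEAE as an AE that "begins or that worsens in severity after at least one dose of the study drug has been administered". It names no comparison operator and no first-dose time.

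Protocol section 8 sets the start of collection: "All adverse events (Serious and non-serious) will be collected from the time of signing of ICF". Protocol 5.2.1 places consent, randomization and the first on-site intake in Visit 1, which may be split in two. Pre-dose and post-dose events can therefore share a calendar date. Protocol 8.6 requires onset time relative to study drug intake to be recorded for each AE; the SAP's TEAE rule does not use it.

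**The concern.** Midnight precedes any dose taken later the same day. If the imputed time feeds the TEAE test, a reaction that follows the first capsule but has no clock time becomes a pre-treatment event. An event about which nothing is known is counted, while one known to fall on the dosing day is not, so better information makes an event less likely to be counted.

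Safety is the only objective left in SAP version 5.0, because the efficacy analyses were removed after the futility decision (SAP 1, 2.2 and 4.13). All the tables by system organ class and preferred term in SAP 4.11.1 and 4.11.2 are TEAE tables. If the drug causes acute first-day reactions, the same rule applied to both arms would remove more events from the active arm and shrink the difference.

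**Working it through.** No figure in the plan depends on this rule, so there is none to reproduce. The check is whether an AE dated on the first-dose day, with its time set to 00:00, meets the TEAE definition.

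**Inputs.** AE time 00:00 (SAP 4.3.1). First-dose time either known, with 10:00 as an illustrative assumption, or missing and itself set to 00:00 under the general rule. The four operators are the possible readings of 'after' in SAP 4.11.1.

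| Comparison | Dose at 10:00 | Dose time missing, set to 00:00 |
|---|---|---|
| Date-time, strictly after | not TEAE | not TEAE |
| Date-time, on or after | not TEAE | TEAE |
| Date, on or after | TEAE | TEAE |
| Date, strictly after | not TEAE | not TEAE |

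The event is lost in 3 of 4 readings when the dose time is known and in 2 of 4 when it is missing. These counts describe readings of the text; they are not probabilities. An AE with no start date is a TEAE in every cell.

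**Does the text select a row?** The only comparison that the SAP spells out is the one for partial dates. It is at date level and does not say whether equality counts. For a complete date with a missing time there is no such sentence, only the 00:00 rule. The AE tables display no clock times and the listings show the time as not known. An imputed time meant for the tabulations therefore matters mainly through a classification, and the TEAE flag is the evident one. This makes a date-time reading plausible but does not establish it.

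**Partial dates.** An unknown day in the first-dose month is moved to the first-dose day, and classification uses date components. Such an event is lost under a date-time test only if 00:00 is then attached through the general rule. That would defeat an imputation that leans towards counting it.

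**What remains visible.** The listing in SAP 4.11.1 covers non-treatment-emergent events, and the overview has rows for any AE and any SAE. Those rows hold the event only nominally: the same section splits AE summaries into first dosing to Day 28 and after Day 28, and an event placed before first dosing falls in neither period.

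**Count.** The documents give no AE counts, no rate of first-day onset and no rate of missing clock times.

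**The case against.** The strongest reply is that the SAP never says these events are dropped. It refers to the first dosing date and names no first-dose time; if none is collected, a true date-time comparison is impossible. Under a date-level on-or-after test nothing is lost. Acute first-dose reactions are also among the events most likely to have known timing, because the first intake is on site and Protocol 8.6 requires onset relative to dosing. All of this stands, and it makes the loss conditional. It does not remove the problem, because the SAP does not choose the harmless reading and its definition says 'after'.

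Three stronger readings are tempting but unsupported:

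- **That these events are dropped, or disappear from the between-arm comparison.** The operator is unstated, and the events stay in the listing and nominally in the non-TEAE overview rows.
- **That partial dates set to the first-dose day share the same fate.** Their own sentence classifies them by date components, and the AE-specific 00:00 rule covers only known dates.
- **That a number of patients can be attached.** Protocol 8.4 reports headache, nausea and vomiting in more than 10% of patients, but across different doses and durations. It adds that frequency seemed dose-related from 75 mg, whereas this trial uses 50 mg. It says nothing about first-day onset. The 533 active patients are the planned number in a trial that was stopped early.

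**Conclusion.** The concern holds in conditional form. The 00:00 rule, read with the TEAE definition, would exclude untimed first-dose-day AEs from the TEAE rows and from all tables by system organ class and preferred term under a date-time comparison with a known dose time, or under any strict 'after'. Under a date-level on-or-after comparison it would not. The SAP leaves the choice open, and its treatment of AEs with no start date points to a conservative intent that the 00:00 rule can contradict.

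The size is unknown and cannot be bounded from the documents. It depends on how many AEs on the first-dose date lack a clock time and on whether a dose time is collected. The point should be settled before the safety tables are produced, because those tables are the main remaining output of the plan.

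**What to change.** In SAP 4.3.1, replace the 00:00 rule for AE start times with:

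> An AE whose start date equals the first-dose date and whose time is unknown is treatment-emergent unless the recorded onset relative to study drug administration shows that it began before the first dose.

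In SAP 4.11.1, state that the TEAE comparison is on or after the first-dose date whenever the time is missing. Say that this also governs partial dates imputed to the first-dose date, so that the general 00:00 rule cannot undo that imputation.

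The cost is two sentences and a small programming change. No new data are needed, since Protocol 8.6 already requires onset relative to dosing. The downside is that a few truly pre-dose events on the same day may be counted; because treatment is blinded, their proportion should be similar in both arms.
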